#### 6.1.4 Analyses for the Secondary Aims - Recurrence of UTI and Predictive Model

The definition of recurrent UTI as a secondary endpoint is that it has to meet the exact same stringent criteria as the index UTI and its onset occurs more than 2 weeks from the last day of treatment for the preceding UTI, or following a negative urine culture. The analytic approach of (1) testing for equivalence of proportion of recurrent UTIs between patients who had VUR and were treated with placebo after their first or second UTI (RIVUR patients) and patients who did not have VUR after their first or second UTI (recruited as patients to this study) and (2) building a predictive model will be identical to the approach described above for the renal scarring outcome.

In comparing differences in recurrent UTI between the two groups we will adjust for known risk factors for recurrent UTI (such as age, gender, race, circumcision status) using multivariable logistic regression models (for recurrent UTI (yes/no)) and Cox Proportional Hazards models (for the time to recurrent UTI). We will also determine whether the 2 groups are different in terms of other factors not known to be associated with recurrent UTI, and we will adjust for those factors as well in order to control for any potential unrecognized confounders.

#### 6.1.5 Safety Analysis

All subjects entered into the study at Visit 1 will be included in the safety analysis. The frequencies of AEs by type, body system, severity will be summarized. SAEs (if any) will be described in detail. This is an observational study and so we will report only AEs and SAEs directly related to the study and not to underlying illness. AE incidence will be summarized along with the corresponding exact binomial 95% two-sided confidence intervals.

#### 6.2 Sample Size and Power

The sample size calculations provided below assume that we will combine data from approximately 150 children in RIVUR and 360 children in CUTIE (N=510). Although the RIVUR study is expected to begin enrollment in March 2007, and this study is planned to commence in Fall 2007, the accrual goals stated below are still expected to be accomplished, as described in Section V.B.3. In order to reduce confounding related to site-specific patient characteristics, we have restricted subjects for comparison to those from the 3 sites participating in both RIVUR and CUTIE, and therefore have chosen not to include all 300 anticipated placebo treated children in RIVUR. However, if there are no significant differences between RIVUR enrolled children from the 3 CUTIE sites and the other sites; we will consider increasing our sample of placebo-treated RIVUR children (and therefore our power) for all analyses. The sample size and power calculations provided below assume the more conservative and smaller anticipated sample. Because of the structure of this study as an ancillary study to the RIVUR study, the sample size is pre-defined. The calculations below show that the specific aims of this study are achievable with this sample size.

Table 6 lists sample sizes needed to test equivalence in the proportion of children who have renal scarring on the outcome DMSA scan among:

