### 3.2.3 Total Number of Study Sites/ Total Number of Subjects Projected

Participants will be recruited from 3 study sites:

- 1) The CHOP Healthcare Network, which includes the wards of the Main Hospital, the Emergency Department, the Radiology Department, 6 Urology Practices, and 33 primary care practices sharing a common electronic health record in the CHOP Healthcare Network. The outpatient practices of the CHOP Healthcare Network span a large geographic area and provide a wide array of primary care and sub-specialty services. In FY 2004 the CHOP Healthcare Network saw a total of 987,342 outpatient visits. CHOP's four primary care centers and one faculty practice provide health services to more than 20,000 area children. The Hospital has also established a network of 28 regional pediatric practices in Pennsylvania, New Jersey, and Delaware called "Kids First," with 153 physicians and total patient panels exceeding 74,000 covered lives. All 33 of these primary care practices are members of a Practice Based Research Network and share a common electronic health record (EPIC).
- 2) The CHP Healthcare Network, which includes the Primary Care Center (22,300 visits annually), the Emergency Department (60,000 visits annually), 18 suburban affiliated community pediatric sites, the Division of Pediatric Urology, and the hospital wards at CHP.
- 3) The CNMC Healthcare Network, which includes five Children's Health Centers and five subspecialty Outpatient Centers located throughout the Washington-metro area, as well as the Emergency Department and hospital wards at CNMC.

The RIVUR protocol stipulates that CHOP and CHP each enroll 120 subjects into the RIVUR study. We anticipate that CNMC, which is part of a larger network of centers in the RIVUR study (represented on the steering committee by Women and Children's Hospital of Buffalo) will contribute 60 subjects to RIVUR. If randomization results in half of these 300 subjects receiving placebo, then there will be 150 subjects from these 3 study sites in the placebo arm of RIVUR.

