The participants in the proposed ancillary study will serve as the comparison group. Each of the sites intends to enroll 120 subjects for a total of 360 subjects in the comparison group. This should not be problematic, even if the study's enrollment period does not overlap completely with RIVUR's, because among children who have had a UTI, approximately 60-70% will not have VUR, so non-refluxing children will outnumber refluxing children by at least 2.5:1. Furthermore, there will be fewer disincentives to enrollment in the ancillary study, as it is observational in nature, involves and does not include randomization to a placebo. For these reasons, we do not anticipate difficulty enrolling 120 subjects per site, even with an anticipated start date up to 1 year into RIVUR's enrollment period.

Combining placebo treated participants from RIVUR and participants in the ancillary study, our sample size will be 510 (150 from RIVUR and 360 from the ancillary study). If, as described in the "Background and Significance" section (1.1), approximately two-thirds of enrolled children will have pyelonephritis and 15-52% of them will develop scars from the index UTI, then approximately 10-35% of children (n=51 to 179) will have some renal scarring during the 2-year study period. This does not take into consideration renal scarring that will develop from recurrent UTIs, which will only serve to increase the proportion of children who have renal scarring at the end of 2 years.

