#### **6.1.2 Analysis plans for Specific Aim 1 – Primary Outcome**

In order to test whether the proportion of children who have renal scarring on DMSA scan is equivalent among the CUTIE study patients who did not have VUR and the placebo-treated RIVUR study who did have VUR, we will calculate the difference in proportions and test whether the difference in proportions is less than 10% or not using a one-sided 0.05 significance level. We will therefore test the null hypothesis that the VUR group and non-VUR group are not equivalent and that the difference in the proportions of renal scarring between the groups is 10% or farther from zero in the same direction. If we reject this null hypothesis, the alternative hypothesis in this case is that the proportions of renal scarring in the two groups are equivalent, closer to each other than a 10% difference. This approach of essentially "reversing" the traditional roles of the null and alternative hypothesis is used to assure that the study is powered to detect equivalence, and not merely to conclude equivalence because differences were not significant on a traditional testing approach [which can occur simply because of a too small sample size]. As a secondary analysis, we will test using the same approach the proportion of children with severe scarring (grades 3 or 4 scarring on at least one kidney). The DMSA is planned to be done at 24 months after the index UTI, but if a DMSA is indicated and done sooner, and shows scarring, that DMSA will serve as the primary outcome.

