If the subjects who agree to enroll in RIVUR differ from those who agree to enroll in CUTIE in ways that are associated with the development of renal scarring, then a comparison of renal scarring in these 2 groups will be confounded by these differences. Although a priori we do not anticipate such differences to emerge, in testing for differences in renal scarring we will adjust for potential risk factors for renal scarring (age, race, gender, fever) using multivariable logistic regression models. We will also determine whether the 2 groups are different in terms of other factors not known to be associated with renal scarring, and we will adjust for those factors as well in order to control for any potential unrecognized confounders. If any adjustment is found necessary to prevent bias, then we will also do hypothesis testing based on the 95% confidence interval of the odds-ratio calculated from the coefficient of the VUR variable in the logistic regression model, testing for equivalence as above.

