**Table 8. Sample size for equivalence testing**

% of A and B with renal scarring on outcome DMSA scan	Sample size
0.10	79+190=269
0.13	100+238=338
0.15	112+269=380
0.20	141+337=477

- 1) Children in the CUTIE study who do not have VUR, and;
- 2) Children in the RIVUR study who do have VUR and are receiving placebo.

All comparisons assume  $\alpha=0.05$  (one-sided for equivalence – difference in proportions farther from zero in the same direction), power=80%, equivalence limit difference in proportions=0.10, expected difference in proportions=0 and ratio of numbers of children in A and B of 150:360 (150 in A and 360 in B) (Table 8). The rate of renal scarring is assumed to be equal in groups A and B, and is estimated in the 10-15% range—in the lower range of previous reports but more consistent with a population with first UTI drawn largely from primary care practices as opposed to subspecialty clinics. Based on

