# Chapter 2: Recruitment, Screening, and Eligibility

## 2.1 Overview

Recruitment and retention of an adequate number of study participants are critical to the success of any observational research study. To try and maximize the number of eligible participants enrolled into the CUTIE study, and to help enroll children from a broader spectrum of severity of illness, CUTIE clinical sites will be recruiting as either primary (acute) care sites, or subspecialty (referral) care sites. This chapter outlines the steps leading up to enrolling a participant into the CUTIE Study.

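### Restriction to three sites leaves unequal site mixes in the two groups, so any CNMC difference in scarring enters the crude Aim 1 test; a site-stratified difference removes it at little cost

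*Protocol*

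**What the plan says.** Section 6.2 recognises site as a source of confounding and gives its answer: "In order to reduce confounding related to site-specific patient characteristics, we have restricted subjects for comparison to those from the 3 sites" shared by RIVUR and CUTIE. It adds that placebo children from the other RIVUR sites may be brought in later if they do not differ significantly.

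Section 3.2.3 sets the targets. For the VUR group, "The RIVUR protocol stipulates that CHOP and CHP each enroll 120 subjects into the RIVUR study", CNMC is expected to add 60, and half of each are expected to be on placebo. For the non-VUR group, "Each of the sites intends to enroll 120 subjects for a total of 360 subjects in the comparison group".

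Section 6.1.2 defines the Aim 1 test: the investigators will "calculate the difference in proportions and test whether the difference in proportions is less than 10% or not using a one-sided 0.05 significance level". No stratification or covariate enters this step. In the next paragraph, "we will adjust for potential risk factors for renal scarring (age, race, gender, fever) using multivariable logistic regression models". Other factors on which the groups turn out to differ are to be adjusted for as well. If adjustment proves necessary, a further equivalence test is based on the 95% confidence interval of the VUR odds ratio. Section 6.1.1 also says, in general terms, that analyses will be adjusted for differences in potential confounders. Site is not named in either section. Section 6.1.4 carries the same approach over to recurrent UTI.

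**The concern.** Restriction gives both groups the same set of sites, but it does not give them the same proportions from each site. If scarring varies by site, a crude pooled difference mixes the VUR contrast with a site contrast. Site is known for every child, so this part of the confounding can be removed without new data.

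The documents give some reason to think that scarring could vary with the recruiting setting. Chapter 2 of the manual (section 2.1) says that "CUTIE clinical sites will be recruiting as either primary (acute) care sites, or subspecialty (referral) care sites", in order to broaden the severity of illness enrolled. Section 6.2 justifies its 10-15% scarring rate by recruitment mainly through primary care rather than subspecialty clinics.

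What is at stake is the error rate at the 10-point margin. An equivalence claim would support the statement that VUR on VCUG does not identify children at risk. A shift towards zero makes that claim easier to reach when it is false; a shift away from zero makes it harder to reach when it is true.

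**Working it through.** **Inputs.** From 6.1.2 and Table 8: one-sided alpha 0.05, "power=80%, equivalence limit difference in proportions=0.10, expected difference in proportions=0 and ratio of numbers of children in A and B of 150:360". From 6.2: scarring about 15%, attrition 10% per year, so 0.9 × 0.9 = 0.81 retained, giving 121.5 and 291.6 children. From 3.2.3: placebo 60/60/30 and CUTIE 120/120/120. Scarring rates by site are not given and are assumed below.

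**The plan's own figure.** With ratio 360/150 = 2.4, n(VUR) = p(1−p)(1 + 1/2.4)(1.645 + 0.842)²/0.10². At p = 0.15 this is 111.67, and × 2.4 = 268.01, total 379.69. Table 8 prints 112+269=380. The other three rows reproduce too, so the calculation is that of a crude, one-sided test.

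**Site mix.** VUR: 60/150, 60/150, 30/150 = 40%, 40%, 20%. Non-VUR: 33.3% each. CNMC's share differs by 13.3 points.

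**Bias.** If CHOP and CHP share one rate and CNMC differs from it by g, the crude VUR minus non-VUR difference is shifted by (0.20 − 0.333) × g = −0.133 × g. It takes a gap of 7.5 points to move the difference by 1 point.

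**Error rate.** I take the test to guard against a VUR excess. The chance of declaring equivalence is Φ((0.10 − d)/SE − 1.645), where d is the expected crude difference and SE² = pV(1−pV)/121.5 + pN(1−pN)/291.6.

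Example: non-VUR rates 10/10/20% and a true VUR excess of 10 points at every site. Then pV = 0.4 × 0.20 + 0.4 × 0.20 + 0.2 × 0.30 = 0.220, pN = (0.10 + 0.10 + 0.20)/3 = 0.133, d = 0.0867 and SE = 0.0425. The result is Φ(0.313 − 1.645) = 0.092, against a nominal 0.05.

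| Rate at CHOP and CHP | CNMC minus the others | Shift in crude difference | False equivalence |
|---|---|---|---|
| 10% | 0 | 0 | 5.0% |
| 10% | +5 points | −0.67 points | 6.9% |
| 10% | +10 points | −1.33 points | 9.2% |
| 10% | +15 points | −2.00 points | 11.8% |
| 10% | +20 points | −2.67 points | 14.8% |
| 15% | −5 points | +0.67 points | 3.6% |
| 15% | −10 points | +1.33 points | 2.5% |

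**Power when the groups are equal within every site.** For the last two rows, the one-sided test has about 80% and 78% power crude, against about 85% and 87% with a site-stratified difference.

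**Cost of stratifying when sites do not differ.** Mantel-Haenszel weights nV·nN/(nV + nN) are 40, 40 and 24, total 104. The crude equivalent is 150 × 360/510 = 105.9. At 15% scarring the full-sample SEs are √(0.1275/104) = 0.0350 and √(0.1275/105.9) = 0.0347. Power is 88.7% stratified against 89.2% crude. With 81% retained it is 82.3% against 82.9%.

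**The case against.** The strongest reply is that the plan already provides for this. Section 6.1.1 says analyses will be adjusted for differences between the groups. Section 6.1.2 commits to adjusting for other factors that differ, including factors not known to affect scarring. On the planned counts the site mixes differ clearly (chi-square 9.07 on 2 df, p = 0.011), so site would probably qualify if anyone looked. This stands in part: a reader might infer that the plan has no route to site adjustment, and that would be wrong. But the odds-ratio test that follows is additional, has no stated odds-ratio margin, and leaves the crude 10-point test in place.

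Second, nothing shows that CNMC differs from CHOP and CHP. The manual does not say which sites recruit as referral sites. Section 3.2.3 describes all three as broad healthcare networks, initial eligibility matches RIVUR's (3.1.1), and DMSA scans are read centrally without knowledge of clinical events (4.1). This also stands. Central reading limits reader differences, though not differences in case mix.

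Third, a reader might infer that a higher CNMC rate costs power to show equivalence. That follows only from two one-sided tests, and the plan states one. Under a single test against a VUR excess, a higher CNMC rate raises crude power to about 94-95% at gaps of 10 to 20 points, as the counterpart of the inflated error. Power is lost when CNMC scars less.

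Finally, section 6.2 claims only to reduce confounding, which restriction does.

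**Conclusion.** The point holds as a conditional weakness that is cheap to remove. The unequal mix follows from the stated targets, and the crude test passes 13.3% of any CNMC gap into the difference compared with the 10-point margin. A 5-point excess at CNMC moves the one-sided error from 5% to about 7%, and a 20-point excess moves it to about 15%. A deficit of 5 or 10 points lowers the error to about 3.6% or 2.5% and costs about 4 or 9 points of power compared with stratifying. With no gap there is no bias.

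These sizes rest on assumed site rates, on target rather than actual enrolment, on 81% retention, on a common rate at CHOP and CHP, and on the test being directed at a VUR excess. If it were directed the other way, the effects of a high and a low CNMC rate would swap. A reader might infer that the Aim 1 result will be biased, or that equivalence will be falsely declared. The documents do not support that, because they give no site rates and no evidence that CNMC differs.

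**What to change.** In 6.1.2, make the Aim 1 estimate a site-stratified risk difference, for example with Mantel-Haenszel weights over the three sites, tested one-sided against the same 10-point margin. Keep the crude difference as supportive. Name site among the adjustment covariates beside age, race, gender and fever. Make the same changes for recurrent UTI in 6.1.4.

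In 6.2, say that restriction equalises the set of sites but not the mix, since CNMC is planned to supply 20% of the VUR group and 33% of the non-VUR group. If placebo children from other RIVUR sites are added, note that half of the 300 would come from sites with no CUTIE children, so they cannot contribute to a within-site comparison.

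The change is to analysis wording only and needs no new data or children. The cost is about 0.5 to 1 point of power if sites do not differ.

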**Table 8. Sample size for equivalence testing**

% of A and B with renal scarring on outcome DMSA scan	Sample size
0.10	79+190=269
0.13	100+238=338
0.15	112+269=380
0.20	141+337=477

- 1) Children in the CUTIE study who do not have VUR, and;
- 2) Children in the RIVUR study who do have VUR and are receiving placebo.

All comparisons assume  $\alpha=0.05$  (one-sided for equivalence – difference in proportions farther from zero in the same direction), power=80%, equivalence limit difference in proportions=0.10, expected difference in proportions=0 and ratio of numbers of children in A and B of 150:360 (150 in A and 360 in B) (Table 8). The rate of renal scarring is assumed to be equal in groups A and B, and is estimated in the 10-15% range—in the lower range of previous reports but more consistent with a population with first UTI drawn largely from primary care practices as opposed to subspecialty clinics. Based on

A distinction should be drawn between serious and severe AEs. A severe AE is a major event of its type. A severe AE does not necessarily need to be considered serious. For example, nausea which persists for several hours may be considered severe nausea, but would not be an SAE. On the other hand, a stroke that results in only a limited degree of disability may be considered a mild stroke, but would be an SAE.

#### 7.3.1 Relationship of SAE to Study Drug or Other Intervention

The relationship of each SAE to the study intervention should be characterized using one of the following terms in accordance with CHOP IRB Guidelines: definitely, probably, possibly, unlikely or unrelated. As this study does not involve an investigational drug, we do not anticipate the need to characterize the relationship of SAEs to study drug.

#### 7.4 IRB/IEC Notification of SAEs

The Principal Investigator will promptly notify the IRB of all study on-site SAEs and other unanticipated problems related to research using the CHOP Internal SAE reporting form and in accordance with the following timeline. External SAEs that are unexpected and related to the study intervention should be reported as they are received using the External SAE form (if applicable).

Table 11: Adverse Event Notification

Type of Internal Adverse Event	Initial Notification (Phone, Email, Fax)	Written Report
Internal (on-site) SAEs Death or Life Threatening	24 hours	Within 5 calendar days
Internal (on-site) SAEs All other SAEs	72 hours	Within 5 calendar days
Unanticipated Problems Related to Research	72 hours	Within 5 calendar days
All other AEs	N/A	Summary of AEs Reported at Time of Continuing Review

#### 7.4.1 Follow-up report

If an SAE has not resolved at the time of the initial report, a follow-up report including all relevant new or reassessed information (e.g., concomitant medication, medical history) will be submitted to the IRB. All SAE will be followed until either resolved or stable.

#### 7.5 Investigator Reporting of a Serious Adverse Event to Sponsor

---

Reporting will be consistent with the requirements of the IRB and the NIH.

#### **7.6 Medical Emergencies**

This is an observational study and so we do not anticipate medical emergencies. The site PIs will work with families to help get their children the care they require in the event of a medical emergency.

### **8 STUDY ADMINISTRATION**

#### **8.1 Data Collection and Management**

##### **8.1.1 Data Management System**

A web-based data management system (DMS) will be used for this study. The data management system will provide all of the capabilities required for research data management, including: data transfer, data entry, data validation, database updating, database closure, data retrieval, data inventory, security and confidentiality, and archiving, and in addition will support randomization.

Each clinical site will be responsible for entering the data it collects. The clinical site staff will use the DMS to enter screening data and eligibility data, run an algorithm to determine eligibility, and for each eligible patient, the DMS will issue a random treatment assignment. Follow-up data will also be entered at the clinical sites into the DMS.

The server and main database reside at the DCC at the Collaborative Studies Coordinating Center (CSCC) at the University of North Carolina at Chapel Hill.

